3.4.1.2 Clinical Laboratory Data

Descriptive statistics will be provided for clinical laboratory data including CMV viremia, presented as both actual values and changes from baseline over time, for the Safety Population. A shift analysis from baseline to the highest post-baseline value for the liver function tests may also be presented. A list of laboratory analytes is included in Appendix B.

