HB-101 uses replication-deficient lymphocytic choriomeningitis virus (rLCMV) as a vector for a bivalent recombinant vaccine against Human Cytomegalovirus (HCMV). One vector expresses the pp65 protein of HCMV, and one expresses a truncated glycoprotein B (gB) protein of HCMV. The 2 vectors are produced separately. The final drug product is manufactured by mixing 1 batch of rLCMV pp65 and 1 batch of rLCMV gB in a 1:1 ratio based on pp65- and gB-expressing vectors. HB-101 was produced pre-diluted and ready-to-use. HB-101 is formulated at 1.2×10^8 FFU/mL. The product is filled in 2 mL single-dose vials containing 0.7 mL of vaccine. Sodium chloride (0.9% w/v) will be used as the placebo. The sponsor will supply this saline for the study.

2.2.4 *Sample Size Determination*

A total sample size of approximately 150 patients is planned for the study. Patients in Groups 1 and 2 will be randomized with a 2:1 ratio for active versus placebo. Patients in Group 3 will be enrolled to receive open-label HB-101. The sample size has been set for an initial assessment of the safety and immunogenicity of the vaccine candidate, which will provide for approximately 100 patients exposed to the HB-101 vaccine. No formal statistical assessment for sample size determination has been conducted. The sample size is considered adequate to provide the necessary safety and immunogenicity data and help with the determination of point estimates of clinical efficacy endpoints (clinically significant CMV infection as defined by the Food and Drug Administration (FDA) "Guidance for Industry: Cytomegalovirus in Transplantation: Developing Drugs to Treat or Prevent Disease") to design and adequately statistically power Phase 3 trials.

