2.3 Study Endpoints

2.3.1 *Primary Endpoints*

For objective of assessing the safety and reactogenicity of HB-101, the primary endpoints are

- Incidence and severity of Adverse events (AEs), serious adverse events (SAEs), and changes in laboratory values
- Incidence and severity of localized or generalized injection site reactions

For objective of assessing the immunogenicity of HB-101, the primary endpoints are descriptive central statistics of the following immunogenicity parameters:

- CMV Neutralization (neut)
- CMV Enzyme-linked immunospot (ELISPOT) phosphoprotein 65 Kd (pp65)
- CMV ELISPOT gB

2.3.2 *Secondary Efficacy Endpoints*

- Incidence and time to clinically significant CMV infection, CMV disease, and CMV syndrome after transplant
- Incidence and time to CMV viremia requiring anti-viral therapy after transplant
- Incidence and duration (in days) of anti-CMV therapy courses (at therapeutic doses) required after transplant
- Incidence and time to quantifiable CMV DNAemia , peak CMV DNAemia level, and duration of CMV DNAemia above the limit of quantitation after transplant
- Incidence and time to graft failure and organ rejection after transplant

2.3.3 *Exploratory Efficacy Endpoints*

Descriptive central statistics of the following immunogenicity parameters:

- CMV Intracellular cytokine staining (ICS) pp65
- CMV ICS gB
- LCMV ELISPOT nucleoprotein (NP)

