3.1.3 Summary Statistics

Continuous variables will be summarized by using the number of non-missing observations, arithmetic mean, standard deviation, median, minimum, and maximum values as descriptive statistics. Categorical variables will be summarized by using the frequency count and the percentage of patients in each category as descriptive statistics. All data will also be listed.

Within each population, results will be presented according to treatment arm and total for Groups 1 and 2 and open-label HB-101 for Group 3 and total for all the three groups unless specified otherwise. Results from Groups 1 and 2 and results from Group 3 will be displayed in separate outputs unless specified otherwise.

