3.4.1 Primary Endpoints

3.4.1.1 Adverse Events (AEs)

AEs will be captured from the date of informed consent through study completion. All AEs will be coded to system organ class and preferred term using the MedDRA version 22.0 and analyzed using the Safety Population. A treatment-emergent adverse event (TEAE) is defined as an adverse event with a start date and time on or after the first administration of study drug and up to 30 days past the last administration of study drug, or after 30 days past last dose and meeting one of the following criteria:

- Serious AE (SAE)
- AE of special interest post-transplant
- AE related to study medication
- AE related to HLA sensitization

Adverse events of special interest post-transplant are graft rejection, CMV syndrome, and CMV disease.

An overview of AEs will be provided including counts and percentages of patients with the following:

- Any AEs
- Any TEAEs
- Any Grade 3 (severe) or higher TEAEs
- Any Grade 3 (severe) or higher TEAEs related to study medication

- Any TEAEs related to study medication
- Any TEAEs of special interest post-transplant
- Any TEAEs of special interest post-transplant and related to study medication
- Any serious AEs (SAEs)
- Any treatment-emergent serious AEs (TE-SAEs)
- Any TEAEs leading to discontinuation of study medication
- Any TEAEs related to study medication leading to discontinuation of study medication
- Any TEAEs related to COVID-19
- Most frequently reported adverse events related to study medication

Both the pre-transplant and post-transplant adverse events and adverse events of above categories will be included in the table summary. The post-transplant adverse event will be summarized by treatment group for Groups 1 and 2 and open-label HB-101 for Group 3.

Counts and percentages of patients will also be presented by system organ class and preferred term for each of the categories in the overview. Counts and percentages of most frequently reported adverse events and most frequently reported adverse events related to study medication may also be displayed in separate tables.

Listings will be presented specifically for SAEs and TEAEs leading to discontinuation of study drug.

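### Laboratory changes are a primary endpoint by incidence and severity, but the committed analysis is continuous summaries only, so no per-arm count or severity category of laboratory change is assured

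*SAP*

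**What the plan says.** SAP Section 2.3.1 lists as a primary safety endpoint: "Incidence and severity of Adverse events (AEs), serious adverse events (SAEs), and changes in laboratory values".

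The analysis is in Section 3.4.1.2, for the Safety Population: "Descriptive statistics will be provided for clinical laboratory data including CMV viremia, presented as both actual values and changes from baseline over time". It continues: "A shift analysis from baseline to the highest post-baseline value for the liver function tests may also be presented". It then points to the analytes: "A list of laboratory analytes is included in Appendix B".

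Section 3.1.3 defines the statistics: "Continuous variables will be summarized by using the number of non-missing observations, arithmetic mean, standard deviation, median, minimum, and maximum values as descriptive statistics". It adds: "All data will also be listed".

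The adverse event overview in Section 3.4.1.1 has a severity cut, "Any Grade 3 (severe) or higher TEAEs", tabulated by system organ class and preferred term. Neither Section 3.4.1.2 nor Appendix B gives a grading scale, a reference-range category, a threshold, or a count of patients with an abnormal or worsened value.

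**The concern.** An incidence is a number of patients out of those at risk, and a severity is a category or grade. Summaries of a continuous value by visit are neither. If the SAP is followed exactly and the optional table is not produced, the laboratory part of the primary safety endpoint has no analysis that yields the named quantity.

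This matters because the sample size was set for an initial assessment of safety and immunogenicity (Section 2.2.4), and Groups 1 and 2 have a placebo arm. The useful laboratory result is how many patients per arm worsened on each test and by how much. Without a required table, that comparison depends on what was reported as an adverse event, or on tables designed after the data are seen.

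**Working it through.** The SAP states no figure on this point, so there is nothing to reproduce. The check is mainly a comparison of the text.

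**1. Endpoint against analysis**

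| Item | Status | Planned output |
|---|---|---|
| Injection site reactions (2.3.1, 3.4.1.3) | primary | incidence and severity, by symptom type and site |
| Laboratory changes (2.3.1, 3.4.1.2) | primary | continuous summaries; optional liver shift |
| Vital signs (3.5.1) | additional safety | continuous summaries |
| Physical examination (3.5.2) | additional safety | counts and percentages |

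The sister primary endpoint has an analysis that matches its wording. Laboratory changes get the same treatment as vital signs, which are not an endpoint.

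**2. Coverage of the optional shift table**

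Appendix B lists 7 liver analytes, 6 hematology lines (counting white cells with differential as one) and 3 renal lines: 7 + 6 + 3 = 16.

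- No categorical output: 6 + 3 = 9 of 16.
- Optional output only: 7 of 16. No shift categories are defined.
- Of those 7, albumin is of concern when it falls, and a shift to the highest value cannot show a fall.

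CMV viremia is also named in Section 3.4.1.2, but its incidence is covered in Section 3.4.2. The gap concerns the Appendix B panels.

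**3. What minimum, maximum and SD can and cannot give**

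Group sizes: "A total sample size of approximately 150 patients is planned for the study". With Group 3 at its 15% minimum and 2:1 allocation, 150 × 0.85 = 127.5 are randomized. Of these, 127.5 × 2/3 = 85 receive HB-101 and 127.5 / 3 = 42.5 receive placebo.

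Illustration with assumed values that are not in the SAP: ALT is 25 U/L with SD 10 in most patients, and k of 85 rise to 200 U/L at one visit.

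- Mean shift = k × (200 − 25) / 85
- SD = √[100 × (85 − k)/85 + (k/85)(1 − k/85) × 175²]

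| k | Incidence | Mean shift (U/L) | SD (U/L) | Maximum (U/L) |
|---|---|---|---|---|
| 1 | 1.2% | 2.1 | 21 | about 200 |
| 3 | 3.5% | 6.2 | 34 | about 200 |
| 5 | 5.9% | 10.3 | 42 | about 200 |

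The planned table would reveal that something happened, through the maximum and the inflated SD. The maximum is the same whether one patient or five are affected, and no column gives the count or a severity. Because the table is by visit, it also cannot show whether extremes at two visits belong to one patient or two.

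**4. Extremes are not comparable between unequal arms**

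Assume the same background rate p of an extreme value in both arms. The chance of at least one is 1 − (1 − p)^n.

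| p | n = 85 | n = 42 |
|---|---|---|
| 1% | 57% | 34% |
| 3% | 92% | 72% |
| 5% | 99% | 88% |

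The larger HB-101 arm shows an extreme more often with no vaccine effect at all. A count with its denominator corrects for this; a minimum or maximum does not.

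**The case against.** The other side has four points of substance.

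- **The summaries are more than means.** Section 3.1.3 adds SD, median, minimum and maximum, and Sections 3.1.3 and 5 promise listings. A reader might infer from Section 3.4.1.2 that individual toxicity is averaged away. The documents do not support that: an extreme value would show at its visit and in the listing. What remains is that neither output counts patients by arm.
- **Adverse event tables count and grade.** A reader might infer that no rate or grade of any laboratory abnormality will be produced. That is too strong. An abnormality reported as an adverse event enters the counts and the Grade 3 or higher rows. The protocol, not shown here, may say which results must be reported. But Appendix A (pre-transplant schedule, footnote 18) has the investigator judge the clinical significance of local results, so a count of reported events is not the incidence of laboratory change. The only severity cut in the overview is Grade 3 or higher.
- **The endpoint could be parsed differently.** If incidence and severity govern only the adverse event terms, laboratory changes stand alone and Section 3.4.1.2 matches. The plain grammar of the single list item favors the other reading. If the narrower one was meant, Section 2.3.1 should say so.
- **The study is descriptive, with documents still to come.** There is no formal testing (Section 3.1.4), and output templates (Section 4.1) and programming specifications (Section 5) are separate. A descriptive study still needs the descriptive quantity that it names. Choosing how a primary endpoint is summarized belongs in the SAP.

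**Conclusion.** The point holds as a mismatch between a primary endpoint and its analysis. Section 3.4.1.2 assures no per-arm incidence or severity of laboratory change. The only categorical output is optional, reaches 7 of 16 listed safety analytes and looks in one direction.

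This rests on the plain reading of Section 2.3.1 and on the SAP text alone. The ALT and background-rate figures are assumptions that show what the planned statistics can convey; they do not predict this trial's data. A reader might go further and infer that a real laboratory signal would be missed. The documents do not support that, because extremes, listings and reported adverse events would all be available. The defect is that the number affected and the severity in each arm would not be tabulated as planned output. It should be corrected before database lock, and it calls no figure in the SAP into question.

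**What to change.** In Section 3.4.1.2, replace the optional liver shift with a required table for each hematology, liver and renal analyte and each arm. The table should:

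- give the number and percentage of patients by baseline category against worst post-dose category, in the harmful direction for that analyte, or both directions where both matter;
- use a grading scale named in the SAP before database lock, or low/normal/high by reference range where no grade exists (Section 3.4.1.1 refers to grades, but the SAP names no scale);
- count worsening from baseline, not any abnormal value;
- show values before transplant separately from those after it.

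The last item is needed because of the visit timing. On the nominal schedule in Table 1, a two-dose patient has the visit 30 days after the last dose at 28 + 30 = Day 58, while transplant may fall anywhere from Day 35 to Day 62. For most of that window the sample is taken after transplant, and a single worst value would mix surgery and immunosuppression with any vaccine effect. Footnote 11 of the pre-transplant schedule also allows for post-injection visits after transplant.

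Keep the continuous summaries as support.

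The cost is SAP wording and a few more tables from samples already in the Appendix A schedule. The small downside is that many patients awaiting a kidney will start with abnormal renal and hematology values, so the baseline categories will be crowded and the tables must be read as worsening.

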Safety blood collection (CBC with differential, liver function tests and enzymes, renal function tests)	X ¹³	X ¹²		X ¹⁸	X ¹²		X ¹⁸	X ¹²		X ¹⁸	X	X
All concomitant medications		X	X	X ¹⁷	X	X	X ¹⁷	X	X	X ¹⁷	X	X ²⁰
Record adverse events		X	X	X ¹⁷	X	X	X ¹⁷	X	X	X ¹⁷	X	X
Record SAEs		X	X	X ¹⁷	X	X	X ¹⁷	X	X	X ¹⁷	X	X
Transplant characteristics											X	

1. After transplant, patients will be assessed per the study visits in Table 6 (all patients of the study who receive study drug). Remaining pre-transplant phone calls/study visits will occur post-transplant and will not be protocol deviations.

2. During the study, it is possible that the time windows of study visits and assessments will be redundant. If the time window is ± 2 weeks, assessments should NOT be duplicated.

3. If kidney transplant occurs prior to Day 34, the patient will be administered study drug (HB-101 or placebo) at Day 0 only. A minimum of 7 days (± 2 days) must be planned between the last dose of study drug and transplantation.

4. If kidney transplant occurs between Day 35 and Day 62, the patient will be administered study drug (HB-101 or placebo) at Day 0 and Day 28. A minimum of 7 days (± 2 days) must be planned between the last dose of study drug and transplantation.
5. If kidney transplant occurs between Day 63 and Day 90 or between Day 91 and Day 120, the patient will be administered study drug (HB-101 or placebo) at Day 0, Day 28, and Day 56 or Day 84. A minimum of 7 days (± 2 days) must be planned between the last dose of study drug and transplantation.
6. There is a ± 3 day window on assessments during the pre-transplant Treatment Period, to take into account public or religious holidays or weather, if not explicitly specified otherwise.
7. During the study, the Screening Period should be within 56 days of Day 0.
8. Time (window) from the last dose of study drug (HB-101 or placebo) is 3 days (± 1 day).
9. Time (window) from the last dose of study drug (HB-101 or placebo) is 7 days (± 3 days).
10. Time (window) of study drug (HB-101 or placebo) is 28 days (± 7 days) from Dose 1 to Dose 2 and 28 or 56 days (± 7 days) from Dose 2 to Dose 3 (depending on the transplant date).
11. In some cases, the post-injection follow-up visits will occur post-transplant.
12. Assessments occur prior to study drug (HB-101 or placebo) injection.
13. Assessments can be conducted for up to 14 days prior to Day 0.
14. Assessments can be conducted for up to 56 days prior to Day 0.

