APPENDIX B: CLINICAL LABORATORY ANALYTES

Liver Function Tests and Enzymes:

Albumin

Alkaline phosphatase

Alanine aminotransferase

Aspartate aminotransferase

Direct bilirubin

γ -glutamyl transpeptidase

Total bilirubin

Endocrinology:

Follicle-stimulating hormone [1]

1. Follicle-stimulating hormone would be conducted for all females aged ≤ 50 years, with 6 months of spontaneous amenorrhea, up to 14 days prior to Day 0.

Serum or urine human chorionic gonadotropin [2]

2. Serum or urine human chorionic gonadotropin would be conducted for all female patients of childbearing potential during the study. Urine testing will be limited to patients producing urine daily.

Hematology

Hematocrit

Hemoglobin

Platelet count

Red blood cell count

White blood cell count with differential [3]

Reticulocyte count

3. Neutrophils, lymphocytes, eosinophils, monocytes, and basophils.

Renal Function Tests

Blood urea nitrogen

Serum creatinine

Chronic Kidney Disease Epidemiology Collaboration [4,5]

4. Defined as glomerular filtration rate = $141 \times \min(\text{Scr}/\kappa, 1)^\alpha \times \max(\text{Scr}/\kappa, 1) - 1.209 \times 0.993^{\text{Age}} \times 1.018$ [if female] $\times 1.159$ [if black] where: Scr is serum creatinine in mg/dL, κ is 0.7 for females and 0.9 for males, α is -0.329 for females and -0.411 for males, min indicates the minimum of Scr/ κ or 1, and max indicates the maximum of Scr/ κ or 1.
5. Central laboratory would calculate glomerular filtration rate.

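### The optional liver-test shift table takes the highest post-baseline value for the whole panel, which is the wrong direction for albumin, one of its seven analytes

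*SAP*

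**What the plan says.** The only shift analysis the SAP describes for laboratory data is in section 3.4.1.2: "A shift analysis from baseline to the highest post-baseline value for the liver function tests may also be presented". The next sentence says where the tests are named: "A list of laboratory analytes is included in Appendix B".

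Appendix B has a panel headed "Liver Function Tests and Enzymes". It contains albumin, alkaline phosphatase, alanine aminotransferase, aspartate aminotransferase, direct bilirubin, γ-glutamyl transpeptidase and total bilirubin. The pre-transplant schedule in Appendix A uses the same panel name for the blood draw: "Safety blood collection (CBC with differential, liver function tests and enzymes, renal function tests". Neither the SAP text nor its appendices give a direction of concern for individual analytes.

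The main laboratory output is separate and is not optional. Section 3.4.1.2 provides descriptive statistics for the laboratory data, "presented as both actual values and changes from baseline over time, for the Safety Population". Section 3.1.3 defines the statistics for continuous variables as the number of observations, "arithmetic mean, standard deviation, median, minimum, and maximum values as descriptive statistics", and adds: "All data will also be listed".

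**The concern.** A shift table on an extreme value shows how many patients moved from an acceptable baseline to their worst later value. It does this only if the chosen extreme lies in the adverse direction. Here one direction is set for a panel that contains an analyte running the other way. Read literally, the rule picks each patient's most favourable albumin, and a programmer following the SAP would have no instruction to do otherwise.

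Changes in laboratory values are part of the primary safety endpoint (section 2.3.1), and section 4.1 carries the same methods into any interim analysis. A reader who sees an albumin row with few or no shifts to low could take it as reassurance, when the row was built in a way that rarely allows such a shift to appear.

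**Working it through.** The plan states no figure on this point, so there is none to reproduce. The check sets the rule beside the analyte list.

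**1. Rule against panel.** The rule in 3.4.1.2 is: baseline category against the category of max(post-baseline values).

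| Appendix B liver analyte | Direction of concern | Is the highest value the worst? |
|---|---|---|
| Alkaline phosphatase | rise | yes |
| Alanine aminotransferase | rise | yes |
| Aspartate aminotransferase | rise | yes |
| Direct bilirubin | rise | yes |
| γ-glutamyl transpeptidase | rise | yes |
| Total bilirubin | rise | yes |
| Albumin | fall | no, it is the best |

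The rule fits 6 of 7 analytes. The directions are ordinary laboratory interpretation; the SAP does not state them.

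**2. Consequence for albumin.** Let L be the lower limit of normal. The maximum is below L only if all k post-baseline values are below L. The minimum is below L if at least one is.

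**3. Number of draws.** In the safety-blood row of Appendix A, the marks after the Day 0 pre-dose draw fall at 7 days after Dose 1, Dose 2, 7 days after Dose 2, Dose 3, 7 days after Dose 3, the day of transplant, and 30 days after the last dose. That is up to k = 7 for a three-dose patient. Without the two Dose 3 visits it is k = 5 for a two-dose patient. With k = 7, six low values and one normal value are displayed as normal.

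**4. Illustration with assumed inputs.** Suppose each draw is independently low with probability p. The SAP gives no such figure, so p is varied from 0.05 to 0.5.

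- Lowest value is low: 1 − (1 − p)^k
- Highest value is low: p^k

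| k | p | Lowest is low | Highest is low |
|---|---|---|---|
| 5 | 0.05 | 0.226 | 3.1 × 10⁻⁷ |
| 5 | 0.20 | 0.672 | 0.00032 |
| 5 | 0.50 | 0.969 | 0.031 |
| 7 | 0.05 | 0.302 | 7.8 × 10⁻¹⁰ |
| 7 | 0.20 | 0.790 | 0.000013 |
| 7 | 0.50 | 0.992 | 0.0078 |

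Worked line: k = 7, p = 0.20 gives 1 − 0.8⁷ = 1 − 0.2097 = 0.790, and 0.2⁷ = 0.0000128.

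**5. Correlated draws.** Independence exaggerates the contrast, so normal values were also simulated with within-patient correlation 0.5 or 0.8, k = 7, low defined as below −1.96 SD, baseline not low, and an assumed fall of 2 SD.

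| Fall | Correlation | Lowest is low | Highest is low |
|---|---|---|---|
| At one visit | 0.5 | 51.9% | 0.01% |
| At one visit | 0.8 | 50.3% | 0.05% |
| At all visits | 0.5 | 88.0% | 12.2% |
| At all visits | 0.8 | 74.9% | 25.6% |

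A transient fall almost never appears in the table as written. A sustained fall appears in part. The sizes depend on the assumptions; the direction does not.

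**The case against.** Four points can be made for the plan.

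- **The table is optional.** This stands. If it is not produced, nothing is affected. If it is produced, the SAP fixes the rule.
- **Falls appear elsewhere.** This also stands, and it sets the limit of the point. A reader might infer that falls in albumin would be lost from the safety report, or that the primary laboratory endpoint is biased toward no signal. The documents do not support that. The required by-visit summaries carry the minimum and the change from baseline, and all data are listed (sections 3.1.3 and 5). Section 3.1.4 rules out formal hypothesis testing, so no formal test turns on this table. Those outputs do not, however, count patients who moved from normal to low, which is the purpose of a shift table.
- **The phrase may mean enzymes and bilirubin only.** The choice of the highest value suggests that the author had such tests in mind, and the reading is possible. But the section does not say so, and the Appendix B heading groups albumin with them. If the narrower meaning was intended, naming the analytes settles it.
- **Details may sit in the programming specifications or output templates.** Sections 4.1 and 5 mention these, and they are not at hand. They might handle albumin properly, so one cannot say that the delivered table would be wrong. They would not correct the rule in the SAP.

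**Conclusion.** Wrong as written, at the lowest severity. One of seven liver analytes is given the wrong direction in one optional table. Under the literal reading, a shift to low albumin is displayed only when every post-baseline value is low.

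The conclusion rests on three assumptions: that the panel named in 3.4.1.2 is the one in Appendix B, that the table uses low, normal and high categories, and that a fall is the direction of concern for albumin. The first is the natural reading but is not spelled out. The probabilities above are illustrations from assumed inputs, not estimates for this trial.

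The point concerns the liver panel only, since no shift table is described for haematology or renal tests.

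**What to change.** In section 3.4.1.2, do one of the following:

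- replace the highest value with the worst value, defined as the highest for enzymes and bilirubin and the lowest for albumin; or
- name the analytes that enter the highest-value shift table and leave albumin out.

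Carry the same choice into the programming specifications and the output template. The table can remain optional, because making it mandatory would not correct the direction. The cost is a few words in the SAP before database lock and about one line of code. No data collection changes.
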